## 9.2. Sample Size Determination

The primary endpoint is Objective tumor response assessed by RECIST version 1.1 per ICR. Analysis of tumor response will be based on both Overall tumor response and on Intra-Cranial tumor response.

OR is defined as a confirmed CR or confirmed PR from the first dose of study treatment until disease progression, start of anticancer therapy or death due to any cause. Both CR and PR must be confirmed by repeat assessments performed no less than 4 weeks after the criteria for response are first met.

ORR is defined as the proportion of treated participants with confirmed CR or confirmed PR per ICR assessment and will be estimated together with its 2-sided exact 95% CI (using an exact Clopper-Pearson CI).

According to literature, platinum-based doublet chemotherapy in patients with ALK + NSCLC refractory to second generation TKIs has an objective response rate of approximately 30%. Setting as target for lorlatinib a response rate of about 43% (as observed in cohort EXP-3B of phase 2 portion of study B7461001), a sample size of 60 participants would result in an exact two-sided 95% CI of the ORR with lower limit of the CI greater than 30%. In order to compensate for a potential 15% drop out rate (participants with death prior to first post-baseline assessment, inadequate baseline assessment, new anticancer therapy started prior to first post-baseline assessment, post-baseline disease assessments missing), the overall sample size for the study is set to 70 participants.

The study will be considered to have met its primary endpoint if the lower limit of the 95% confidence interval around the estimated ORR excludes 30%.

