#### 9.3. Populations for Analyses

For purposes of analysis, the following populations are defined:

Population	Description		
Enrolled	All participants who sign the ICF		
Intent to Treat (ITT)/Safety	All enrolled participants who take at least 1 dose of lorlatinib		

Population	Description
Per Protocol Population: Participants with CNS metastases based on Independent Central Review	Subset of the ITT analysis set including only participants with CNS metastases at study entry (i.e. with Lesions having Disease Site=Brain) according to Independent Central Review
Per Protocol Population: Participants with CNS metastases based on Investigator Assessment	Subset of the ITT analysis set including only participants with CNS metastases at study entry (i.e. with Lesions having Disease Site=Brain) according to Investigator Assessment

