3. ENDPOINTS AND BASELINE VARIABLES: DEFINITIONS AND CONVENTIONS

3.1. Primary Endpoint

3.1.1. Confirmed OR by ICR

Objective Response (OR) based on ICR assessment is defined as complete response (CR) or partial response (PR) according to RECIST v1.1 from date of first dose until documented PD or start of new anti-cancer therapy without regard to discontinuation from treatment. Both CR and PR must be confirmed by repeat assessments performed no less than 4 weeks after the criteria for response are first met.

Participants without a CR or PR or with death prior to first post-baseline assessment, inadequate baseline assessment, new anti-cancer therapy started prior to first post-baseline assessment, and all post-baseline disease assessments missing will be considered as non-responders.

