5.1. Hypotheses and Decision Rules

5.1.1. Hypotheses and Sample Size

According to literature, platinum-based doublet chemotherapy in participants with ALK + NSCLC refractory to second generation TKIs has an objective response rate of approximately 30%. Setting as target for lorlatinib a response rate of about 43% (as observed in cohort EXP-3B of phase 2 portion of study B7461001), a sample size of 60 participants would result in an exact two-sided 95% CI of the ORR with lower limit of the CI greater than 30%. In order to compensate for a potential 15% drop out rate (participants with death prior to first post-baseline assessment, inadequate baseline assessment, new anti-cancer therapy started prior to first post-baseline assessment, post-baseline disease assessments missing), the overall sample size for the study is set to 70 participants.

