6. ANALYSES AND SUMMARIES

6.1. Primary Endpoint

6.1.1. Confirmed OR by ICR

Analysis set: ITT: All enrolled participants who take at least 1 dose of Lorlatinib

Analysis methodology:

• Objective Response Rate (ORR) defined as the percentage of patients with a confirmed best overall response (BOR) of CR or PR according to RECIST v1.1

BOR will be determined based on reported overall responses at different evaluation timepoints by the independent radiologist from the date of treatment start until documented disease progression or start of new anti-cancer therapy, according to the following rules:

- CR = at least two determinations of CR at least 4 weeks apart and documented before progression and start of new anti-cancer therapy
- PR = at least two determinations of PR or better (and not qualifying for a CR) at least 4 weeks apart and before progression and start of new anti-cancer
- SD (for patients with at least one measurable lesion at baseline) = at least one SD assessment (or better and not qualifying for CR or PR) ≥ 6 weeks after date of treatment start and before progression and the start of new anti-cancer therapy
- Non-CR/Non-PD (for patients with only non-target disease at baseline) = at least one Non-CR/Non-PD assessment (or better and not qualifying for CR or PR) ≥ 6 weeks after date of treatment start and before progression and the start of new anti-cancer therapy
- PD = progression ≤ 14 weeks after date of treatment start and not qualifying for CR, PR or SD
- Not Evaluable (NE) = all other cases.

Clinical deterioration will not be considered as documented disease progression.

- patients without documented CR or PR will be considered as non-responders
- Exact CI for a binomial proportion for ORR using the Clopper-Pearson method
- best % changes vs baseline as defined below under Summaries used for Reporting DMB02-GSOP-RF02 4.0 Statistical Analysis Plan Template 01-Nov-2018 PFIZER CONFIDENTIAL Page 24 TMF Doc ID: 98.03

• % change vs baseline across visits as defined below under Summaries used for Reporting

Intercurrent events and missing data:

- data on response after subsequent anti-cancer therapy is administered will be excluded
- participants with death prior to first post-baseline assessment, inadequate baseline assessment, new anti-cancer therapy started prior to first post-baseline assessment, and all post-baseline disease assessments missing will also be considered as non-responders.

Summaries used for reporting:

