- The frequency (number and percentage) of patients with BOR of CR, PR, SD, PD, non-CR/non-PD (applicable only to patients with non-measurable disease at baseline), and NE (not-evaluable)
- ORR estimated by dividing the number of patients with OR (CR or PR) by the number of patients in the ITT population
- corresponding exact 2-sided 95% CIs
- Waterfall plots of best %change vs baseline
 - A waterfall plot of maximum percent reduction in the sum of longest diameter for nonnodal lesions and short axis for nodal lesions from baseline will be created. These plots will display the best percentage change from baseline in the sum of the diameter of all target lesions for each patient with measurable disease at baseline and at least one valid post-baseline assessment. The best percent change from baseline will be calculated from start of study treatment up to first visit with disease progression or to the last visit available prior to the start of new anti-cancer therapy (for patients who start new antitumor therapy prior to progression or who are progression-free patients at the time of analysis)
- Spider Plots of %change from baseline across visits
 - A spider plot of %change from baseline across visits in the sum of longest diameter for non-nodal lesions and short axis for nodal lesions from baseline will be presented. These plots will display the % change from baseline in the sum of the diameter of all target lesions for each patient with measurable disease at baseline and at least one valid postbaseline assessment. The % change from baseline will be calculated from start of study treatment to each visit up to first visit with disease progression or to the last visit available prior to the start of new anti-tumor therapy (for patients who start new antitumor therapy prior to progression or who are progression-free patients at the time of analysis).

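### The sample size is raised from 60 to 70 to make up for drop-outs whom the primary analysis keeps in the denominator as non-responders, so the reason given for 70 does not match the analysis.

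*Protocol*

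**What the plan says.** **Size.** Protocol 9.2 takes about 30% as the chemotherapy response rate and about 43% as the target for lorlatinib, from cohort EXP-3B of the earlier study. It says that "60 participants would result in an exact two-sided 95% CI of the ORR with lower limit of the CI greater than 30" per cent. It then adds participants: "In order to compensate for a potential 15% drop out rate (participants with death prior to first post-baseline assessment, inadequate baseline assessment", together with new anti-cancer therapy before the first post-baseline assessment and missing post-baseline assessments. SAP 5.1.1 repeats this and concludes that "the overall sample size for the study is set to 70 participants".

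**Analysis.** Protocol 9.2 itself states that "ORR is defined as the proportion of treated participants with confirmed CR or confirmed PR per ICR assessment". Protocol 9.3 defines the ITT set as "All enrolled participants who take at least 1 dose of lorlatinib". SAP 3.1.1 lists the same four categories, ending with the statement that participants with "all post-baseline disease assessments missing will be considered as non-responders". SAP 6.1.1 repeats the rule ("all post-baseline disease assessments missing will also be considered as non-responders") and gives the calculation: "ORR estimated by dividing the number of patients with OR (CR or PR) by the number of patients in the ITT population". No response-evaluable set is defined. The two sets labelled per protocol are only the subsets with CNS metastases.

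**Decision.** Protocol 9.1 and 9.2 and SAP 5.1.2 declare success if the lower 95% limit for the response rate lies above 30%.

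**The concern.** Dividing a sample size by one minus the drop-out rate makes sense when drop-outs are removed from the analysis and a set number must remain. Here they stay in the denominator and can only count against the drug. The sizing sentence therefore describes an evaluable-only analysis that the plan does not perform.

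The study has a formal pass/fail rule, and 70 is the number on which it is judged. Someone reading 9.2 would conclude that up to 15% non-evaluable participants can be absorbed with the criterion still met at the target rate. Whether that is so depends on what the 43% measures, which the documents leave open. Neither document states the probability of meeting the rule, so the drop-out sentence is the only assurance on offer.

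**Working it through.** **Inputs.** Exact two-sided 95% Clopper-Pearson interval, reference rate 30%, target about 43%, base size 60, drop-out 15% and final size 70 (Protocol 9.2). 12 responders of 28 in the earlier cohort (Protocol 2.2). ITT denominator (Protocol 9.3, SAP 6.1.1).

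**Formulas.** Lower limit for x of n: the 2.5% quantile of Beta(x, n − x + 1). Upper limit: the 97.5% quantile of Beta(x + 1, n − x). Pass mark c(n): the smallest x with a lower limit above 30%. Probability of success: P(X ≥ c) for X ~ Binomial(n, p).

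**Step 1: the plan's own figures.** 26/60 = 43.3% has a 95% interval of 30.6% to 56.8%, so the criterion is met; 25/60 has a lower limit of 29.1% and fails. For the inflation, 60/0.85 = 70.6 and 60 × 1.15 = 69. Both 60 and 70 reproduce.

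**Step 2: the rule as it will be applied with 70 treated.** 29/70 has a lower limit of 29.8% and fails. 30/70 = 42.9% has an interval of 31.1% to 55.3% and passes. The pass mark is 30. If 10 of the 70 are non-evaluable, those 30 responders must come from 60 evaluable participants, which is 50.0% and not 43.3%.

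**Step 3: the two readings of 43%.**

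- *All-treated rate.* Drop-outs are already inside the 43%. Sixty treated participants meet the plan's criterion at 26/60, so no inflation is needed. The probability of success at a true 43% is 52.9% with 60 treated and 55.5% with 70.
- *Evaluable-only rate.* 26 responders among 60 evaluable, plus 10 non-responders, give 26/70 = 37.1%, with an interval of 25.9% to 49.5%: a miss. With a share d non-evaluable, the ITT rate is 0.43 × (1 − d). The 15% is the plan's figure; 5% and 10% are assumed here to show a range.

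| Non-evaluable share d | ITT rate | P(success), n = 60 | P(success), n = 70 |
|---|---|---|---|
| 0% | 43.0% | 52.9% | 55.5% |
| 5% | 40.9% | 39.5% | 41.0% |
| 10% | 38.7% | 27.1% | 27.5% |
| 15% | 36.6% | 16.9% | 16.5% |

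On this reading, going from 60 to 70 recovers almost none of what drop-out takes away.

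**Step 4: other operating characteristics at n = 70.** At a true 30%, P(success) = 1.5%. A probability of 80% needs a true ITT rate of 47.2%.

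**Step 5: if the number treated is not exactly 70.** Protocol 4.1 plans 70 assigned, while ITT requires a dose.

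| Treated | 65 | 66 | 67 | 68 | 69 | 70 | 71 | 72 |
|---|---|---|---|---|---|---|---|---|
| Pass mark | 28 | 28 | 29 | 29 | 29 | 30 | 30 | 30 |
| P(success) at 43% | 54.3% | 58.4% | 52.8% | 57.0% | 61.0% | 55.5% | 59.5% | 63.4% |

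The probability is a saw-tooth in n, so 55.5% is one point in a range of about 53% to 63%.

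**The case against.** The best defence has four parts.

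- *The target may already absorb drop-out.* Twelve of 28 reads like an all-treated rate, and Protocol 4.2 says 28 were included. On that reading, 70 does allow for drop-out, and ten participants come on top. This stands. A reader might infer that the sample size makes no allowance for drop-out at all; the documents do not support that, because it is true only if 43% is an evaluable-only rate. Nor do they support the opposite as fact: neither document says how non-evaluable participants were counted in EXP-3B.
- *The study aims at precision.* Protocol 4.2 says so, and 70 delivers it: the interval width falls from 38.4 points (12/28) to 24.2 points (30/70). The sentence about 60 participants is conditional on the target being observed, and 26/60 satisfies it. This stands, and no power is claimed that could be called wrong. But 9.1, 9.2 and SAP 5.1.2 also set a pass/fail rule, so its probability is useful supplementary information.
- *Saying that extra participants never help is too absolute.* This also stands. At an ITT rate of 36.6%, P(success) is 16.9% for 60, 20.5% for 69, 16.5% for 70 and 21.7% for 72. The gain is small and erratic, and 70 falls in a trough.
- *Counting non-evaluable participants as non-responders is conservative.* Agreed. That supports the analysis, not the reason given for 70.

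None of this rescues the compensation sentence: on one reading it is unnecessary, and on the other it does not work.

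**Conclusion.** The stated reason for 70 does not match the planned analysis. The four categories that the extra participants are meant to offset are the four that stay in the ITT denominator as non-responders.

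The practical weight depends on an unstated fact. If 43% is an all-treated rate, which 12 of 28 suggests but does not prove, the defect is a superfluous sentence and 70 is harmless. If it is evaluable-only, the compensation fails, and 15% non-evaluable participants would leave about a 17% chance of meeting the rule at n = 70. A reader might take that 17% as the study's expected chance of success. The documents do not support this; it is a conditional worst case.

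Nor is there support for reading 60 or 70 as miscalculated, or the response-rate estimate as biased: both numbers reproduce, and the chance of passing at a true 30% is 1.5%. This is a fault of justification that should be corrected, not a fault of the estimate or the rule. The probabilities assume independent participants with a common response rate and, except where a range is shown, exactly 70 treated.

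**What to change.** Keep 70, the endpoint, the analysis and the decision rule. In Protocol 9.2 and SAP 5.1.1, delete the sentence on drop-out compensation and put in its place:

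> With 70 treated participants (ITT; non-evaluable participants count as non-responders), the criterion is met with at least 30 confirmed responders (42.9%; exact 95% CI 31.1% to 55.3%). If the true ITT ORR is 43%, the probability of meeting it is about 56% (about 53% to 63% for 65 to 72 treated); a true ITT ORR of about 47% is needed for 80% at n = 70. If the number treated differs, the rule applies to the actual ITT number.

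The sponsor should also state whether the 43% from EXP-3B is an all-treated or an evaluable-only rate. Only if it is evaluable-only, add that 5%, 10% or 15% non-evaluable participants would lower the probability at n = 70 to about 41%, 28% or 17%.

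The cost is wording in two sections, with no extra participants. The downside is that the stated operating characteristics look less favourable than the present text implies.

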#### 9.3. Populations for Analyses

For purposes of analysis, the following populations are defined:

Population	Description		
Enrolled	All participants who sign the ICF		
Intent to Treat (ITT)/Safety	All enrolled participants who take at least 1 dose of lorlatinib		

Population	Description
Per Protocol Population: Participants with CNS metastases based on Independent Central Review	Subset of the ITT analysis set including only participants with CNS metastases at study entry (i.e. with Lesions having Disease Site=Brain) according to Independent Central Review
Per Protocol Population: Participants with CNS metastases based on Investigator Assessment	Subset of the ITT analysis set including only participants with CNS metastases at study entry (i.e. with Lesions having Disease Site=Brain) according to Investigator Assessment

# 9.4. Statistical Analyses

The statistical analysis plan will be developed and finalized before database lock and will describe the participant populations to be included in the analyses, and procedures for accounting for missing, unused, and spurious data. This section is a summary of the planned statistical analyses of the primary and secondary endpoints.

## 9.4.1. Efficacy Analyses

Endpoint	Statistical Analysis Methods
Primary	
 
Confirmed OR by ICR
 
Population: ITT
 
Using an exact method based on binomial distributions, estimate the confirmed ORR by ICR and corresponding two-sided 95% CI, based on OR from the time of first dose until progression is met or subsequent anti-cancer therapy is administered without regard to discontinuation from treatment. Participants with death prior to first post-baseline assessment, inadequate baseline assessment, new anti-cancer therapy started prior to first post-baseline assessment, and all post-baseline disease assessments missing will be considered as
 

Secondary	Confirmed OR by INV  • Population: ITT  Use the same statistical analysis methods as for the primary endpoint except that the treatment effect is based on INV.  Confirmed IC-OR by ICR  • Population: Per protocol population of participants with CNS metastases based on Independent Central Review

Endpoint	Statistical Analysis Methods				
	Using an exact method based on binomial distributions, estimate the confirmed IC-ORR by ICR and corresponding two-sided 95% CI, based on intra cranial OR from the time of first dose until intra cranial progression is met or subsequent anti-cancer therapy is administered without regard to discontinuation from treatment. Participants with death prior to first post-baseline assessment, inadequate baseline assessment, new anti-cancer therapy started prior to first post-baseline assessment, and all post-baseline disease assessments missing will be considered as non-responders.				
	TTR by ICR/INV and IC-TTR by ICR/INV				
	• TTR is defined as the time from first dose to first documentation of objective tumor response (CR or PR) that is subsequently confirmed. For patients whose OR proceeds from PR to CR, the onset of PR is taken as the onset of response. TTR will only be calculated for the subgroup of patients with a confirmed objective tumor response.				
	All the analyses will be repeated also for Time to Intracranial Response (IC-TTR) considering patients with intracranial response (i.e. Best Overall Intracranial Response as confirmed Complete Response (CR) or confirmed Partial Response (PR) considering only the Lesions having Disease Site=Brain).				
	TTR and IC-TTR will be summarized based on both ICR and derived investigator assessments using descriptive statistics.				
	DOR by ICR/INV				
	• Using the Kaplan-Meier method, estimate its associated statistics on DOR (including the median DOR with two-sided 95% CI) for responders to lorlatinib, without regard to discontinuation from treatment unless new anti-cancer therapy is initiated or extended gap in tumor assessment is present prior to progression or death. DOR is defined as the time from first documentation of OR (CR or PR) that is subsequently confirmed to the date of first documentation of PD or death due to any cause, whichever occurs first.				
	This analysis is based on responders only from the ITT population. Participants with an event more than 12 weeks (24 weeks post the first 42 weeks) after the last adequate tumor assessment will be censored on the date of the last adequate tumor assessment prior to the gap that documented no progression. If a new anti-cancer therapy starts prior to an event, the participant will be censored on the date of the last adequate tum or assessment that documented no				

Final Protocol, 22  Endpoint	Statistical Analysis Methods				
1	progression prior to start of the new anti-cancer therapy. The CI for the median DOR will be calculated according to Brookmeyer and Crowley method.				
	IC-DOR by ICR/INV				
	• Using the Kaplan-Meier method, estimate its associated statistics on IC-DOR (including the median IC-DOR with two-sided 95% CI) for intra cranial responders to lorlatinib, without regard to discontinuation from treatment unless new anti-cancer therapy is initiated or extended gap in IC tumor assessment is present prior to progression or death. IC-DOR is defined as the time from first documentation of IC-OR (CR or PR) that is subsequently confirmed to the date of first documentation of intra cranial PD or death due to any cause, whichever occurs first.				
	This analysis is based on intra cranial responders only from Participants with CNS metastases populations. Participants with an event more than 12 weeks (24 weeks post the first 42 weeks) after the last adequate tumor assessment will be censored on the date of the last adequate tumor assessment prior to the gap that documented no progression. If a new anti-cancer therapy starts prior to an event, the participant will be censored on the date of the last adequate tumor assessment that documented no progression prior to start of the new anti-cancer therapy. The CI for the median DOR will be calculated according to Brookmeyer and Crowley method.				
	TTP by ICR/INV				
	• Using the Kaplan-Meier method, estimate its associated statistics on TTP (including the median TTP with two-sided 95% CI, the TTP rates at clinically meaningful timepoints with two-sided 95% CI) for all participants who received at least one dose of lorlatinib without regard to discontinuation from treatment unless death occurs, new anti-cancer therapy is initiated or extended gap in tumor assessment is present prior to progression. TTP is defined as the time from date of first dose to the date of the first documented PD.				
	This analysis is based on ITT population. Participants with an event more than 12 weeks (24 weeks post the first 42 weeks) after the last adequate tumor assessment will be censored on the date of the last adequate tumor assessment prior to the gap that documented no progression. If the participant dies before progression, the participant will be censored on the date of death. If a new anticancer therapy starts prior to an event, the participant will be censored on the date of the last adequate tumor assessment that				

Endpoint	Statistical Analysis Methods				
	documented no progression prior to start of the new anti-cancer therapy. Participants with inadequate baseline assessment or with a adequate post-baseline tumor assessments within 12 weeks after the start date will be censored on the start date, unless the participant dies within 12 weeks of the start date, in which case, the patient who be censored on date of death. The CI for the median TTP will be calculated according to Brookmeyer and Crowley method, and the CIs for the survival function estimates at the timepoints will be derived using the log(-log) method.				
	PFS by ICR/INV				
	• Using the Kaplan-Meier method, estimate its associated statistics of PFS (including the median PFS with two-sided 95% CI, the PFS rates at clinically meaningful timepoints with two-sided 95% CI) for all participants who received at least one dose of lorlatinib without regard to discontinuation from treatment unless new anti-cancer therapy is initiated or an extended gap in tumor assessment is present prior to progression or death. PFS is defined as the time from date of first dose to the date of the first documented PD or death due to any cause, whichever occurs first.				
	This analysis is based on ITT population. Participants with an event more than 12 weeks (24 weeks post the first 42 weeks) after the last adequate tumor assessment will be censored on the date of the last adequate tumor assessment prior to the gap that documented no progression. If a new anti-cancer therapy starts prior to an event, the participant will be censored on the date of the last adequate tumor assessment that documented no progression prior to start of the new anti-cancer therapy. Participants with inadequate baseline assessment or with no adequate post-baseline tumor assessments within 12 weeks after the start date will be censored on the start date, unless the participant dies within 12 weeks of the start date, in which case, death will be an event on date of death. The CI for the				
	median PFS will be calculated according to Brookmeyer and Crowley method, and the CIs for the survival function estimates at the timepoints will be derived using the log(-log) method.				

